#### **Secondary Aim - Histology**

A secondary goal will be examine all aspects of histological injury including neuronal such as myelin depletion and nerve swelling, vascular such as intima thickening and cellular hypertrophy, and GL-3 deposition. This will be completed by obtaining deep specimen biopsies of the mucosa and submucosa for analysis of the histopathology of the gastrointestinal tract in symptomatic patients with Fabry disease who are treatment naive or with only <6 months of treatment.

The specimens will be obtained by a clinically warranted sigmoidoscopy and will include an additional deeper endoscopic mucosal resection. Tissue analysis will include evaluation of abnormalities of cellular structure and morphology with correlation with gastrointestinal complaints for each patient and comparison against age matched non-Fabry patient tissue. The hypothesis is that patients will have abnormal findings on histology, which will correlate with the subjects symptoms and findings of on the questionnaires.

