#### **Recruitment Procedures**

Patients will be recruited via the Massachusetts General Hospital lysosomal storage disease clinic. The study will be presented to all patients with Fabry disease who have had gastrointestinal symptoms within the past year. Additionally, we will contact physicians who care for Fabry patients via email and conferences to inform them of the study. If patients indicate they are interested in the study to their provider, the patient may be contacted if the provider refers the patient to the study staff. Flyers with the research coordinator's contact information will also be given to interested patients and providers at conferences. At conferences, if interested, patients will be given the opportunity to sign a form that would allow them to be contacted by the study staff to learn more about the study. Subjects identified through RPDR will

receive a recruitment letter signed by the PI and the patient's provider (Please refer to the Protocol Summary for additional information). We expect to enroll all patients over a two-year period.

1. SmartPill study and questionnaires regarding gastrointestinal symptoms, quality of life and psychiatric comorbidities (Please see “study procedures” for additional information) will be administered to approximately 50 patients.
2. Histology section – Recruit up to 15 treatment naive patients or patients with less than 6 months of therapy who have lower GI symptoms including abdominal pain and/or bowel movement alterations for which a sigmoidoscopy would be clinically warranted. An endoscopic evaluation with mucosal resection will be performed.

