### **Sigmoidoscopy and Endoscopic Mucosal Resection (Visit 4)**

This study visit should take about 3.5 hours to complete.

This study visit consists of a sigmoidoscopy with biopsies and an endoscopic mucosal resection. When additional workup of gastrointestinal symptoms is warranted for altered bowel habits and/or abdominal pain, a subset of 15 treatment naive patients or with less than 6 months of treatment will be recruited from those who completed the SmartPill study for a sigmoidoscopy with biopsy collection and additional endoscopic mucosal resection.

The patient will fast the night prior and receive 2 enemas the morning of the procedure. The patient will present for completion of a clinically needed sigmoidoscopy with routine rectal and sigmoid biopsy collection. In addition, an endoscopic mucosal resection will be completed in the rectum. Biopsies will be sent to pathology for the following analysis.

1. Light microscopy with hematoxylin and eosin, periodic acid schiff, toluidine blue and acetylcholine staining.
2. Electron microscopy
3. Immunohistochemistry staining with anti-Gb3 monoclonal antibody.

All specimens will be examined for cellular morphology, other significant noted injury or structural abnormalities and location of deposition. The biopsies will be specifically analyzed for vascular and neuropathic changes. The specimens will be assessed for presence or absence of neuronal swelling, myelination, vascular sclerosis, intimal fibrosis and hypertrophy of the smooth muscles of the arterioles. The neurological and vascular cells will be assessed for deposition and quantification will be determined based on a degree of deposition scale used previously for renal biopsy analysis in Fabry disease (0 No deposit, +deposit present in a few cells, ++ deposits present in some cells, +++ deposits present in many cells) (Valbuena et al., 2008). Finally, results of analysis of all specimens will be compared to healthy aged-matched controls obtained from banked specimens in the pathology department. Once the analysis is completed, results will be correlated with the patient's gastrointestinal symptom presentation.

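### The histology plan specifies no masking of the reader to Fabry or control status, symptoms or SmartPill results, although the outcomes are graded by eye

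*Combined protocol and SAP*

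**What the plan says.** The Visit 4 section sets out the readings. Deposition in neurological and vascular cells is scored 0, +, ++ or +++, in words only: "deposits present in some cells, +++ deposits present in many cells". No counts or percentages separate the grades. The structural findings are yes/no calls: "The specimens will be assessed for presence or absence of neuronal swelling, myelination, vascular sclerosis, intimal fibrosis", together with arteriolar smooth-muscle hypertrophy. No thresholds are given.

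The readings serve two purposes. They are "compared to healthy aged-matched controls obtained from banked specimens in the pathology department", and "Once the analysis is completed, results will be correlated with the patient's gastrointestinal symptom presentation". The histology aim states the expected result: "The hypothesis is that patients will have abnormal findings on histology, which will correlate with the subjects symptoms".

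On numbers, Recruitment Procedures says "Recruit up to 15 treatment naive patients or patients with less than 6 months of therapy who have lower GI symptoms". The number of controls is not given. Biostatistical Analysis offers descriptive statistics and regression in Fabry patients. It names no case-control test and makes no provision about readers.

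**The concern.** Every histology outcome is a visual judgement with a stated expected direction. The Fabry tissue comes from clinical procedures on symptomatic patients ("The patient will present for completion of a clinically needed sigmoidoscopy with routine rectal and sigmoid biopsy collection"), while the controls are drawn separately from the department's bank. Nothing in the plan prevents a reader from knowing which slide is which. In the standard visit order SmartPill comes before the resection, so symptom and motility data can already exist when slides are read.

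A reader who knows the group may resolve borderline calls towards abnormal in Fabry tissue. A reader who also knows a patient's symptoms may grade towards them. Regression on the resulting grades cannot separate reader expectation from disease.

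The background section presents the lack of comparison with control specimens as a gap in earlier work, and another secondary aim would build an evaluation protocol partly on the histologic findings. The readings therefore need to be credible.

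**Working it through.** **1. Is masking provided anywhere?** Two places might supply it.
- Monitoring and quality assurance describes coded data. That coding applies to results shared with the sponsor, not to slides given to the reader.
- Visit 4 places the symptom correlation after the analysis. This fixes the order of steps; it does not keep symptoms from the reader.

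No section mentions coded or mixed slides. The accurate statement is that masking is not specified.

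**2. Figures in the plan.** The only derived sample size is for motility: 25/0.70 = 35.7 (stated as 35) and 35/0.70 = 50. It has no bearing on histology, so there is no histology calculation to reproduce. What follows is illustration.

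**3. Present/absent calls.** From the documents: 15 cases, the maximum. Assumed: 15 controls, no true difference, true prevalence p of 10 to 30%, two-sided 0.05, Fisher's exact test. A truly negative Fabry specimen is called positive with probability u, and controls are read correctly. The observed probability in cases is p + (1 − p)u; for p = 0.10 and u = 0.30 it is 0.10 + 0.90 × 0.30 = 0.37. The false-positive rate is the sum, over all pairs of counts (a, b) with Fisher p ≤ 0.05, of Bin(a; 15, p + (1 − p)u) × Bin(b; 15, p).

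| True p | u = 0 | u = 0.2 | u = 0.3 | u = 0.5 |
|---|---|---|---|---|
| 0.10 | 0.5% | 12.2% | 26.7% | 64.1% |
| 0.20 | 1.7% | 7.6% | 15.7% | 44.7% |
| 0.30 | 1.7% | 5.2% | 10.6% | 32.2% |

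For u of 0.2 to 0.3 the range is about 5 to 27%, against 0.5 to 1.7% without bias. With 30 controls the ranges are 2 to 3% at u = 0, 12 to 30% at u = 0.2 and 23 to 52% at u = 0.3.

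**4. Symptom correlation.** Spearman test within 15 Fabry patients, no true correlation, simulated.
- One-step upgrading of Fabry slides regardless of symptoms: about 5% for upgrade probabilities of 0 to 0.5. Knowing the group alone does not inflate this test.
- One-step upgrading only of patients with above-median symptoms (true grades 40/30/20/10%): about 7 to 8% at probability 0.3 and about 11% at 0.5.
- Upgrading above-median and downgrading below-median patients (true grades 10/30/30/30%): about 12% at 0.3 and 24% at 0.5.

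**5. Deposition contrast.** With identical true grades of 40/30/20/10% in 15 cases and 15 controls, upgrading 0, 20, 30 or 50% of Fabry slides by one grade gives Mann-Whitney false-positive rates of about 5%, 7%, 11% and 22%. That null gives 60% of healthy controls some deposit, which is hard to credit in a disease that the background defines by this accumulation. If about 95% of controls are instead grade 0 (an assumption) and the Fabry grades stay as above, the test rejects in about 96 to 97% of runs with no reader bias and in about 99% or more with 20 to 30% upgrading. Reader bias then adds little to the conclusion.

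**The case against.** A reader might infer that the slides will be read unmasked. The documents do not say so. They say that biopsies go to pathology, without stating how they are labelled or whether the reader sees symptom data or knows the hypothesis. The omission is certain; the bias is only possible.

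A reader might also infer that knowing the group biases both the control comparison and the symptom correlation. The check does not support that. The correlation is inflated only if grading follows each patient's symptoms, which is a further assumption. Nor is the deposition difference likely to be made by the reader.

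The tests and the control number used here are not in the plan, so the error rates show how the bias would work and do not predict the study's own.

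Coding may also mask imperfectly. Anti-Gb3 staining, the zebra-like bodies described in the background, and the depth of a mucosal resection can each reveal Fabry tissue. This stands as a limit on masking to disease status. It does not apply to symptoms, questionnaires or SmartPill results, which can be withheld. Finally, biased grades are not beyond repair: if slides are kept, a coded re-read could correct them.

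**Conclusion.** The point holds as an omission that should be corrected before any slide is read. The plan relies on subjective grades for a control comparison and a symptom correlation, and specifies no masking for either.

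Exposure is greatest for the present/absent neuronal and vascular calls: about 5 to 27% false positives instead of about 0.5 to 2%, under the assumptions of 15 against 15, no true difference, 10 to 30% prevalence and 20 to 30% of true negatives called positive. For the symptom correlation the rate is about 7 to 11% under the milder symptom-linked model and 12 to 24% under the stronger one, each for a probability of 0.3 to 0.5. The deposition contrast is probably robust.

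The consequences are confined to a secondary aim in up to 15 patients. The primary motility aim is unaffected.

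**What to change.** Add to the Visit 4 section that:
- the coordinator gives each case and control slide a random code and mixes the two sets in common reading batches;
- the pathologist doing the research read has no group, symptom, questionnaire or SmartPill data until the grades are locked;
- linkage to group and symptoms follows the lock;
- routine clinical reads proceed separately.

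The cost is relabelling and batching slides from up to 15 cases plus controls, with no added patients, procedures or readers. Research reading must wait for batches to be assembled. The plan should acknowledge that masking to disease status may be incomplete, for the reasons given above, and that masking to symptoms and SmartPill data is expected to hold.

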### **Patients Travelling from Out of State**

Prior to scheduling the visit, the patient will be provided with an electronic copy of the consent form in accordance with Partners Information Security guidelines. They will be advised to read it over. The study staff will then contact the patient after a couple days and answer any questions the patient may have about the study and can be put in contact with the physician. The patient will be notified of all medications that needs to be stopped for the SmartPill and if eligible, for the sigmoidoscopy. All information for the sigmoidoscopy will be sent to the patient and the subject can be put in contact with a physician to answer any additional questions. If the patient agrees, the condensed visit will be scheduled.

The scheduled visit will be a condensed visit consisting of visit 1 and visit 2. The patient will be provided with information regarding mailing the receiver back to the study staff.

If the patient is eligible for the EMR, the visit will be condensed into 2 days. On the first day, the scheduled visit will include the screening visit (visit 1) and the sigmoidoscopy and EMR (visit 4). The patient will be consented by the physician prior to conducting the medical history and physical and completing the questionnaires. After, the patient will be prepped for the sigmoidoscopy and EMR. On the second day, the SmartPill visit will be conducted. This option will also be available for patients who are in state but cannot travel to the hospital multiple times.

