### Prohibited Medications for SmartPill

1. No medications which may alter gastric pH around the time of the study, which includes:
  - a. Proton Pump Inhibitors for 1 week (examples: omeprazole, lansoprazole and esomeprazole, pantoprazole, rabeprazole)
  - b. Histamine2 Blockers for 3 days [(examples: cimetidine (Tagamet HB), famotidine (Pepcid), and ranitidine hydrochloride (Zantac), nizatidine (Axid)]

- c. Antacids for 1 day (examples: Maalox, Mylanta, Amphogel, Tums, Rolaids)
2. No medications that affect gastrointestinal motility for 3 full days before the start of the study and during the 5 ensuing days of study including but not limited to those drugs listed below:
  - a. Prokinetic agents, such as metoclopramide (Reglan), tegaserod (Zelnorm), domperidone (Motilium), erythromycin, zithromycin, cisapride
  - b. Anti-emetics agents, such as phenergan, compazine
  - c. Narcotic analgesic agents, such as methadone, fentanyl, percocet
  - d. Anticholinergic agents for IBS – Bentyl, Levsin
  - e. Medications for constipation, including enemas, cathartics, polyethylene glycol solutions (including Miralax), and lactulose (e.g., enulose). Patients with constipation may take medications to help stimulate a bowel movement with either milk of magnesia, 2.4 to 4.8 grams (30-60 ml), or magnesium citrate, 11 to 25 grams daily in 1 or more doses, up to 48 hours prior to SmartPill ingestion.
  - f. 5HT3 antagonists, such as Lotronex (alosetron hydrochloride) and Zofran (ondansetron hydrochloride).
  - g. Anti-diarrheal agents, such as Kaopectate (attapulgit, donnagel, rheaban), Pepto-Bismol (bismuth subsalicylate), Imodium (loperamide), and lomotil (atropine diphenoxylate).
  - h. Opiate agents used to treat diarrhea.

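### On the two-day visit option, bowel-preparation enemas precede the SmartPill by about 24 hours; on the better reading this is inside the plan's own 3-day washout, and the analysis does not flag it

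*Combined protocol and SAP*

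**What the plan says.** The section Patients Travelling from Out of State compresses the visits of an EMR-eligible patient into two days. Day 1 holds screening and the procedure. Once consent, history, examination and questionnaires are done, "After, the patient will be prepped for the sigmoidoscopy and EMR". Then "On the second day, the SmartPill visit will be conducted". The arrangement is not confined to travellers: "This option will also be available for patients who are in state but cannot travel to the hospital multiple times". The same section carries the SmartPill medication stops over to these patients: "The patient will be notified of all medications that needs to be stopped for the SmartPill and if eligible, for the sigmoidoscopy".

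The section on Visit 4 sets the preparation: the patient fasts overnight and is to "receive 2 enemas the morning of the procedure".

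Prohibited Medications for SmartPill, item 2, reads "No medications that affect gastrointestinal motility for 3 full days before the start of the study and during the 5 ensuing days of study", and continues "including but not limited to those drugs listed below". Item 2e lists enemas, under drugs for constipation. Its one shorter limit, 48 hours, is for milk of magnesia or magnesium citrate. SmartPill Study Procedure restates the enema restriction as at least 72 hours, again worded for patients with constipation.

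The ordinary schedule runs the other way round. The Follow Up Visit (Visit 3) comes 5 to 7 days after the capsule, and EMR is booked within the 3 weeks after that.

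Biostatistical Analysis specifies descriptive statistics and univariate and multivariate regression relating motility, histology and symptoms. It says nothing about recordings begun inside the washout.

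**The concern.** The ordinary schedule keeps the capsule recording clear of the bowel preparation. The two-day option reverses the order and leaves one night between them, while the washout asks for three full days. Staff who follow the option exactly would therefore produce recordings that the plan's own medication rule appears to rule out, and nothing in the dataset or analysis would identify them.

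Colon emptying time and contractility are part of the primary aim, and these are the measures that an enema could most plausibly disturb. The exposure is also concentrated. Only EMR patients can use the option, and only they contribute both histology and motility data, so the motility-histology regression is the most exposed analysis.

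The same reordering has a separate safety consequence. The only stated pregnancy test is placed under Preparation for Study Visit 2. On the two-day option Visit 2 comes after the sedation and EMR, so nothing requires a test before them, although pregnancy is an exclusion.

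**Working it through.** **Required interval.** Item 2 gives 3 full days: 3 × 24 = 72 h. This agrees with the 72 hours in SmartPill Study Procedure.

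**Scheduled interval.** Enemas are on day 1 and ingestion is on day 2. The documents give no clock times, so these are assumed:
- Enemas between 07:00 and 13:00. The upper end allows for preparation following screening.
- Ingestion between 07:00 and 12:00, since it follows an overnight fast.

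| Case | Interval | Short of 72 h |
|---|---|---|
| Shortest (13:00 to 07:00) | 24 + 7 − 13 = 18 h | 72 − 18 = 54 h |
| Central (same clock time) | 24 h | 72 − 24 = 48 h |
| Longest (07:00 to 12:00) | 24 + 12 − 7 = 29 h | 72 − 29 = 43 h |

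No pair of clock times on consecutive days can reach 72 h. The 48 h magnesium limit does not cover enemas, and the interval would miss that too, by 48 − 29 = 19 h to 48 − 18 = 30 h.

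**Other orders.** Swapping the two days would put the enemas within the 5 recording days, which the same rule covers. On the ordinary schedule the EMR follows Visit 3, 5 to 7 days after ingestion, so the conflict does not arise.

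**Reach.** Recruitment Procedures gives about 50 SmartPill patients and up to 15 histology patients. Uptake *k* of the two-day option is not stated. Taking the full 15 in the histology subset:

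| *k* | Share of 50 recordings | Pairs outside the window (15 − *k*) |
|---|---|---|
| 0 | 0% | 15 |
| 5 | 10% | 10 |
| 10 | 20% | 5 |
| 15 | 30% | 0 |

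**Sample size.** The Power section runs 25/0.70 = 35.7 (stated as 35), then 35/0.70 = 50. It rests on gastric emptying time and uses no colonic measure or washout input, so N = 50 does not change.

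**Histology against symptoms.** On the two-day option the questionnaires are completed before the preparation, so the enemas do not affect that correlation.

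**The case against.** The strongest reply is that the washout does not reach these enemas. Item 2e and SmartPill Study Procedure name enemas only as treatment for constipation, the Visit 4 section does not say what the enemas contain, and the two-day option is a specific provision that sets its own order. A reader might infer an explicit breach of the protocol; the text does not go that far. Against the reply, item 2 is written for any medication that affects motility, with an open list. The two-day section also applies the SmartPill stops to these patients and makes no exception. Applying the washout is therefore the better reading, and an intended exemption would still need a sentence.

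The second reply is that no effect has been shown. That stands. The documents give neither size nor direction. The capsule reaches the colon some time after ingestion, so the gap from enema to colonic recording is longer than 24 h by an unstated amount. Nothing in the documents links preparation enemas to gastric or small-bowel emptying. A reader might infer that the primary results as a whole, or the sample size, are compromised; the documents do not support that.

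The third reply is that the Visit 4 section recruits the histology subset from patients who have already completed the SmartPill study, so few or none may take the option. That also stands: 15 is a ceiling, and zero is equally consistent with the text. Nor is the analysis silent on this issue alone, since Biostatistical Analysis describes no handling of deviations at all.

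On pregnancy, a reader might infer that the test is scheduled too late. In fact its timing before Visit 2 is left open: a test at day-1 screening would comply, but it is not required. Retesting before EMR on the ordinary schedule is a different question.

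**Conclusion.** The concern holds in limited form and should be fixed. The dates are certain: consecutive days cannot provide 3 full days. That the washout applies to preparation enemas is the better reading rather than explicit text. On that reading the interval is about 48 h short, or 43 to 54 h under the assumed clock times.

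The exposure falls mainly on colonic transit and contractility and on the motility-histology regression, with 0 to 15 of about 50 recordings and 0 to 15 of up to 15 pairs involved. It would be wrong to conclude that the results are biased, or in which direction; the documents establish only that the plan could not identify or examine the affected recordings. N = 50 and the histology-symptom correlation are untouched. The pregnancy-test gap on the two-day path is real but separate, and adds no weight to the washout point.

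**What to change.** 1. State in Prohibited Medications for SmartPill, and in the two-day section, whether bowel-preparation enemas count toward the 3-day rule.
2. On the two-day option, record the hours to ingestion from the enemas and from any sedative on the prohibited list (the sedation agent is not named; fentanyl is on the list). Flag recordings begun inside the window and keep them.
3. In Biostatistical Analysis, report colonic motility and motility-histology results with and without flagged recordings, giving the number flagged.
4. Where the patient can stay, offer SmartPill first or a gap of 3 full days, as an option only. With enemas on day 1, the capsule moves to day 4 (72 h) or day 5 (3 full calendar days between). With the capsule on day 1 and 5 to 7 days of recording, EMR moves to about day 6 to 8. Making this mandatory would burden the patients for whom the option exists, in a study whose Power section already cites limited availability.
5. Separately, on the two-day path, require the urine pregnancy test at day-1 screening, before sedation and EMR.

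The cost of items 1 to 3 and 5 is one clarifying statement, one data field, one sensitivity analysis and an earlier urine test. The analysis without flagged recordings may have few motility-histology pairs, or none if all 15 take the option; giving the number flagged makes that visible.
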